Human Studies: In clinical studies, adolescent tobacco smokers experience cognitive deficits which are exacerbated during acute nicotine withdrawal and are more than twice as likely to develop depression by their late 20's.^{32,33} While understudied, results from the human neuroimaging literature largely parallel preclinical findings. Adolescent tobacco smokers (compared to non-smokers) exhibit alterations in hippocampal and cortico-striatal-limbic circuits that map onto executive control (ECN), default mode (DMN), and salience (SN) brain networks, and show notable structural, functional, and connectivity alterations in diverse brain regions enriched for nAChRs including the hippocampus, prefrontal cortex, insula, anterior cingulate (ACC), posterior cingulate (PCC), parietal cortex, cerebellum, thalamus, and striatum.^{11,12,34-38}

Are the Developmental Effects of Vaped Nicotine Similar to Those of Smoked Tobacco?

Little is known about the effects of vaped nicotine on brain function and connectivity in humans and *no neuroimaging studies have been conducted in young people who chronically vape nicotine.* At the time of proposal submission three studies have been published examining the effects of nicotine vaping in humans (all in adults). Acute administration of vaporized nicotine appears to alter the BOLD fMRI signal in the same nAChR-enriched brain regions that cigarette smoke inhalation does.^{39,40} In the first fMRI study conducted in chronic e-cigarette using adults, Nichols *et al.*⁴¹ found evidence for changes in brain activity in response to vaping cues in the

Abbreviated Title: Mindfulness and Teen Vaping

Version Date: 07/21/2025

NIH IRB#: IRB001855

parahippocampal gyrus, PCC, precuneus, fusiform gyrus, lingual gyrus, thalamus, and cerebellum along with multiple parietal, temporal, and occipital regions. *Given the rising rates of nicotine vaping and conflicting messages about the comparative health risks from vaping and smoking, it is of critical importance to determine the effects of vaped and smoked tobacco on brain development and cognitive and emotional outcomes.*

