Neurobiological Models of Adolescent TUD and Mindfulness Identify Overlapping Neural Circuitry. Neuroimaging studies in adults have reliably shown changes in the hippocampus, ACC, PCC, insula, supramarginal gyrus (SMG), and PFC along with DMN, ECN, and SN networks following MT and practice.^{14,51-58} These brain regions/networks show significant anatomic overlap with the brain regions/networks showing evidence of dysfunctional signaling in tobacco using youth.³⁵⁻³⁷ Of significant relevance to our proposal, impairments in hippocampal-prefrontal circuits are observed in TUD samples³⁰ and are strengthened in non-smokers following MT.^{59,60} Additionally, in d-rsFC studies, tobacco smoking adults show altered d-rsFC with fewer state transitions during abstinence^{61,62}; Conversely MT is associated with increased state transitions in non-smoking adolescents and adults.^{63,64} Taken together, these findings indicate that MT impacts neural function, connectivity, and flexibility in a manner that is opposite to the effects of chronic tobacco exposure, suggesting a possible brain mechanism via reversal or ‘normalization’ of dysfunctional networks. Janes *et al.*⁶⁵ recently showed that smartphone app-delivered MT reduced cue-induced PCC activity with the magnitude of reduction in PCC activity predicting concurrent decline in smoking in adults. Alternatively, MT could improve abstinence via compensatory or training mechanisms by strengthening connectivity in unaffected networks.

Abbreviated Title: Mindfulness and Teen Vaping

Version Date: 07/21/2025

NIH IRB#: IRB001855

In this pilot study we will investigate whether measures of s-rsFC and d-rsFC in circuits altered by chronic nicotine exposure are modulated by MT and characterize how such rsFC changes relate to vaping behavior.

Psychological Mechanisms of Mindfulness Training: Awareness & Emotion Regulation

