5.6 Lifestyle Considerations

Participants will be instructed to abstain from cannabis, alcohol, and other street drugs for 24 hours and limit caffeine for 12 hours, prior to scan visits, but will be allowed to vape as usual. Abstinence will be verified on scan days via self-report, and UDT, with participants rescheduled if they test positive for THC or other drugs on UDT and fail a clinical assessment for intoxication. Participants in the vaping group will need to agree to participate in the MBSR training. One parent/guardian must be present for the consent process for participants under 18 y/o, and they will have the option to remain at NIDA while their minor is participating.

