Per regulations, abbreviated IDEs (NSR device studies) do not require an application to the FDA as the IRB acts as FDA's surrogate for review, approval, and continuing review of these type of device studies.

At scan visits:

- Participants will present to the NIDA-IRP BRC for a medical update, and an MRI safety screen, conducted by the MAI/designee or research nurse. They will also complete a nursing evaluation (weight, urine drug test, urine pregnancy test, urine cotinine test, breath CO, and ALC test), and will orient to the MRI scanner. Participants will then undergo a ~60 min MRI session on a Siemens 3.0T MRI scanner using a 32-channel head coil.
- Participants will be instructed to abstain from cannabis, alcohol, and other drugs for 24 hours and limit caffeine for 12 hours prior to scan visits. They will be instructed to continue

Abbreviated Title: Mindfulness and Teen Vaping

Version Date: 07/21/2025

NIH IRB#: IRB001855

nicotine products as usual. Abstinence will be verified on scan days via self-report, and UDT (listed above), with participants rescheduled if they test positive for drugs on UDT and have signs of acute intoxication (per clinical assessment).

- Scan sessions will include: (1) anatomical MRI for registration (T1W), (2) resting-state scan (whole-brain T2*w gradient-echo EPI sequence) [10 minutes, eyes-open, fixation cross], (3) Diffusion Tensor Imaging (DTI).

Follow-up Assessments

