8.3 Safety Assessments

Pre-scan assessments:

- Medical update (e.g., height, weight, change in previously provided history, etc.)
- MRI Safety Screen
- Pregnancy test (females of childbearing potential)

Post-scan assessments:

- Assess for wellbeing

No results will be discussed with participants unless something requires referral for medical follow-up.

Safety monitoring: At each scan visit to NIDA, participants are queried about their general medical and emotional health (including current medications and drug use history) since their last visit to NIDA and are observed throughout each visit at NIDA by study investigators. Any change in health status is noted by protocol staff and evaluated for relevance to the participant's participation. Study staff will communicate with participants during the scan and any who want to terminate the scan for any reason will be allowed to. Investigators will refer the participant to the MAI for any medical adverse events or questions about recent medical conditions.

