9.4.2 Analysis of the Primary Endpoints

Behavioral data analysis: Group differences (Vaping vs. TD) will be evaluated via chi-squares, independent t-tests (Primary Endpoint 1). In addition to EOT nicotine abstinence, Δ scores will be calculated for each behavioral measure (e.g. vaping frequency, emotion regulation) and will be used for within-subject analyses to characterize MBSR-related behavioral change (Primary Endpoint 2).

rsFC fMRI data analysis: Seed-based ROI whole-brain rsFC analyses between *a priori* defined hippocampal seed regions and large-scale brain networks (focusing on DMN, ECN, SN). Whole-brain regression analyses will be conducted for each seed on each individual's preprocessed data resulting in a Fisher-transformed z-value in each brain voxel (**DV**). Seed regions: Right- and left-whole and sub-region hippocampal ROI seeds such as those defined via probabilistic voxel maps created by Chase *et al.*⁹⁹ will be used for rsFC analyses. Target network identification: Hypothesis-driven seed-based analyses will be constrained to voxels within each of three functionally generated masks of large-scale brain networks (DMN, ECN, SN) identified via group independent component analysis⁶ or taken from a published atlas.

s-rsFC Analysis: Independent and Paired t tests will examine group (Vaping vs. TD) (Primary Endpoint 1) and session (Pre/Post-MBSR) (Primary Endpoint 2) effects in s-rsFC strength between each hippocampal seed and voxels within each of the 3 network masks (e.g., seed-ECN voxels).

d-rsFC Analysis: d-rsFC will be estimated using a sliding window method^{21,22} creating windowed correlation matrices, to which a k-means clustering algorithm will be applied to identify states.⁶ Independent and Paired t-tests will examine group (Vaping vs. TD) (Primary Endpoint 1) and session (Pre vs. Post-MBSR) (Primary Endpoint 2) differences in d-rsFC DVs: state occupancy and transitions.

Correlational analyses: To test relationships between MBSR-related Δ rsFC and Δ vaping behaviors and other behavioral outcomes, we will use regression analyses.

Post-hoc analyses: Post-hoc ROI seed-based whole-brain connectivity analyses will test if the regions showing mindfulness-related Δ rsFC are distinct from or overlap with regions modulated by nicotine exposure (from Primary Endpoint 1).

Abbreviated Title: Mindfulness and Teen Vaping

Version Date: 07/21/2025

NIH IRB#: IRB001855

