9.4.5 Baseline Descriptive Statistics

Tobacco vaping and other drug use measures: Tobacco vaping/e-cigarette use (vaping days, vapes/vaping day) and other drug use in the past 28 days will be collected via TLFB at baseline and post-MBSR MRI follow-up visit. Additional information on time to first vape, nicotine concentration used, vape device used, use of flavors, social influence will be collected along with validated instruments measuring e-cigarette dependence (EDS).

Biochemical measures of drug use: Semi-quantitative urine cotinine testing and carbon monoxide (CO) monitoring will be used to verify self-reported post-MBSR abstinence. Urine drug testing, and breath alcohol level will be collected.

Other self-report assessments: Self-report measures of mood, anxiety, coping, emotion regulation, cognitive function and mindfulness found to show changes following MT in prior studies will be collected and used in theory-driven exploratory analyses.

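### Hours since last nicotine use are not scheduled to be recorded at either scan or used in the connectivity analyses, so a fall in vaping after MBSR could make the pre/post change partly one of scan-day nicotine state

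*Combined protocol and SAP*

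**What the plan says.** Nicotine before scans. Section 5.6 and the scan-visit procedures in section 8.2 ask for 24 hours without cannabis, alcohol or other drugs and for limited caffeine. Nicotine is left free: "limit caffeine for 12 hours, prior to scan visits, but will be allowed to vape as usual". The scan-day check by self-report and urine drug test concerns that abstinence request.

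Nicotine state and the endpoints. Section 2.2 says "Acute administration of vaporized nicotine appears to alter the BOLD fMRI signal in the same nAChR-enriched brain regions" that smoke inhalation affects, and that "tobacco smoking adults show altered d-rsFC with fewer state transitions during abstinence". State transitions are one of the dynamic connectivity measures in both primary endpoints (section 3).

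What is recorded:
- At both scan visits the nursing evaluation includes "urine drug test, urine pregnancy test, urine cotinine test, breath CO, and ALC test" (section 8.2). The stated purpose of two of these is narrower: "Semi-quantitative urine cotinine testing and carbon monoxide (CO) monitoring will be used to verify self-reported post-MBSR abstinence" (section 9.4.5).
- At scan visits "participants are queried about their general medical and emotional health (including current medications and drug use history) since their last visit to NIDA" (section 8.3).
- The timeline follow-back (TLFB) covers vaping days and vapes or puffs per day. Section 9.4.5 places it at the post-MBSR MRI visit. Table 1 marks it, and the Craving Questionnaire, for Visits 1 and 12-15 but not for Visit 11, which is scan 2.
- The nearest timing item is in section 9.4.5: "Additional information on time to first vape, nicotine concentration used, vape device used". It asks about the first vape, not the last one before a scan.

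Analysis. Section 9.4.2 uses paired t-tests for the pre/post contrast, and then: "To test relationships between MBSR-related Δ rsFC and Δ vaping behaviors and other behavioral outcomes, we will use regression analyses". No scan-day nicotine covariate is named in 9.4.1 or 9.4.2. Only vapers are scanned twice, and all of them are assigned to MBSR.

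**The concern.** The plan expects vaping to change by scan 2. Section 9.1 hypothesizes that connectivity change predicts vaping change, and section 9.4.3 makes change in vaping frequency at the scan 2 session the primary efficacy outcome. For a teen who has cut down, vaping as usual before scan 2 may mean a longer gap since the last nicotine than at scan 1. Drug state in the scanner would then move with the outcome.

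Two Endpoint 2 results are exposed: the paired contrast, and the regression of connectivity change on vaping change. A change in either could come from MBSR acting on the network, from a different nicotine state at scan 2, or from both. The plan has no repeat-scanned group without MBSR and no recorded interval since last use to help tell these apart. The interval cannot be reliably recovered after the scan.

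**Working it through.** The plan states no figure on this point, so there is none to reproduce. The check has two parts.

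**1. Does any existing measure already supply scan-day state?**

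| Measure | At both scans? | Gives hours since last use? | Named as covariate in 9.4.1-9.4.2? |
|---|---|---|---|
| Urine cotinine (semi-quantitative) | yes | no | no |
| Breath CO | yes | no | no |
| Drug-use query, section 8.3 | yes | not specified | no |
| TLFB | Visit 1; at scan 2 the sections conflict | no, day-level at best | no |
| Craving Questionnaire | Visit 1; at scan 2 only if Visit 11 is combined with Visit 12 or 13 | no | no |

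Exposure is therefore partly measured. The interval since last use is not scheduled, and none of these measures enters the connectivity tests as a state covariate.

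**2. How large could the effect be?** The documents give no size for a nicotine-state effect on connectivity, so these inputs are assumptions, apart from n.
- n = 40 vapers (section 9.2).
- No MBSR effect on connectivity.
- Pre/post correlation 0.5, so the residual SD of change is √(2(1 − 0.5)) = 1.
- A share p of teens moves from recent use to no recent use between scans (20-40%). Each move shifts that teen's change score by d (0.3-0.8 SD).

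Mean shift = p·d. SD of change = √(1 + d²p(1 − p)). The rejection rate comes from the noncentral t with 39 df and noncentrality √40 × mean/SD.

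| d | p | Mean shift | SD | Noncentrality | Rejects at 5% | Rejects at 0.002 |
|---|---|---|---|---|---|---|
| 0.3 | 20% | 0.06 | 1.007 | 0.38 | 6.6% | 0.3% |
| 0.5 | 30% | 0.15 | 1.026 | 0.92 | 14.7% | 1.3% |
| 0.8 | 40% | 0.32 | 1.074 | 1.88 | 45% | 9.4% |

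The 0.002 column matters because section 9.2 cites that level as closer to a cluster-corrected threshold. The 5% column fits a single dynamic-connectivity test rather than a voxelwise map.

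Two-way switching lowers the rate. With d = 0.5 and 30% switching one way, 10% switching back gives a mean shift of (0.30 − 0.10) × 0.5 = 0.10 and a rejection rate of about 9%. With 20% switching back the mean shift is 0.05 and the rate about 6%. This is plausible, because section 5.1 admits teens who vape on as few as 10 of 30 days, and some may have no recent use at scan 1.

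Regression of connectivity change on vaping change, by simulation with n = 40 and a 5% test. Switching drives both variables, and vaping change = b × switch + N(0,1).

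| d | p | b | Association at p<0.05 |
|---|---|---|---|
| 0.3 | 20% | 2 | about 7.5% |
| 0.5 | 30% | 2 | about 15% |
| 0.8 | 40% | 2 | about 36% |
| 0.5 | 30% | 1 | about 9% |
| 0.5 | 30% | 0.5 | about 6% |

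**The case against.** The case for the plan is a fair one.

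- Letting teens vape as usual is a coherent choice, and nothing here argues for changing it.
- Nicotine exposure is not unrecorded. Cotinine and CO are taken at both scans, drug use since the last visit is asked about, and section 9.4.5 puts a TLFB at the post-MBSR scan. Visit 11 may be combined with Visit 12 or 13, when craving and TLFB are due, and section 8.2 aims to complete scan 2 and the first assessments within about a week of training. A reader might infer that scan-day nicotine is wholly undocumented; the documents do not support that.
- Reduced vaping may be a real route by which MBSR acts. Adjusting for nicotine state conditions on a post-treatment variable and can remove true effect. Cotinine is also listed in section 9.4.3 as a measure of the vaping outcome, so adjusting the change-on-change regression for it would be circular. Both points stand and limit the remedy.
- A reader might infer that teens who cut down will show fewer state transitions, which would hide a benefit. The cited finding is in adult smokers during abstinence, so it does not settle the direction for adolescents who reduce vaping.
- For Endpoint 1, recent use in users only is inherent in comparing users with non-users. Splitting 40 vapers by time since last use also runs into section 9.4.7, which regards subgroup analyses as unlikely to be possible.
- This is an uncontrolled open-label pilot, so causal attribution of a pre/post change is limited anyway.

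What remains is narrower: the interval since last use is not scheduled at either scan, and no scan-day nicotine state enters the Endpoint 2 models.

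**Conclusion.** The point holds in that narrow form. If vaping falls after MBSR, the Endpoint 2 paired change and its regression on vaping change may partly reflect nicotine or abstinence state at the scan, and the plan as written offers no direct check.

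Direction and size are unknown. Under the stated assumptions, a single 5% paired test with no MBSR effect rejects in about 7-45% of trials. That falls to about 0.3-9% at p<0.002, and falls further if some teens switch the other way. The spurious regression rate is about 7.5-36% with an assumed 2 SD link between switching and vaping change, and lower with a weaker link. If vaping and its timing do not change, the problem is small.

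These figures illustrate sensitivity; they do not estimate bias in this trial. They do not show that an observed change would be an artefact, or that an MBSR effect should be claimed only if it survives adjustment.

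**What to change.** - Leave the nicotine instruction as it is. At both scans, record the clock time of the last vape and of the last cigarette.
- Give the Craving Questionnaire at Visit 11 when that visit is not combined with Visit 12 or 13.
- Reconcile Table 1 with section 9.4.5 on whether the TLFB is done at Visit 11.
- In section 9.4.2, keep the planned paired contrast and change-on-change regression as the main Endpoint 2 results. Report beside each a sensitivity analysis adjusted for change in time since last nicotine use. Do not adjust the regression for cotinine, and do not make the adjusted result a gate for claiming an effect. If the two results differ, state that the change cannot be separated from nicotine state at the scan.
- For Endpoint 1, only describe time since last use among vapers.

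The cost is one short question at each scan, a questionnaire of 1-5 minutes at some scan 2 visits, and one extra model per Endpoint 2 result. The drawback is that the adjusted estimate may remove true effect that runs through reduced vaping, which is why it is a sensitivity analysis only.

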5.7 Screen Failures

Screen failures are defined as participants who consent to participate in this study but are not subsequently entered in the study. Individuals who do not meet the criteria for participation in this trial (screen failure) because of meeting one or more exclusion criteria that are likely to change over time may be rescreened. Examples include stabilization of antidepressant treatment of an

Abbreviated Title: Mindfulness and Teen Vaping

Version Date: 07/21/2025

NIH IRB#: IRB001855

affective disorder resulting in three months stable dose without significant clinical symptoms. Rescreened participants will be assigned the same participant number as for the initial screening.

5.8 Strategies for Recruitment and Retention

Recruitment is generally conducted under the NIDA IRP Office of the Clinical Director (OCD). Recruiting materials may be developed in-house or by contractors. We may also use the service provided at the NIH Office of Patient Recruitment. All advertising methods will comply with the most current regulations (NIH and OHSRP guidelines) and the NIDA policy on recruitment materials and with Information Systems Security Officer (ISSO) approval for any IT-related tools or metrics to aid in or monitor recruitment. Digital ads link to the Prescreening Form on REDCap. Participants have the option of filling out the Screening Form independently, or leaving a number and receiving a call from the study team, to complete the form as a Phone Screen. Subjects may be recruited from the general population in the Baltimore region through advertising in city, regional or campus newspapers, social media and other online platforms (e.g., Craigslist), email and digital listservs, direct mail, local clubs and/or schools, and other media or via direct outreach and referrals. Please refer to the Recruiting Materials document for more information about recruitment methods. Participants may be recruited online and from the concurrent vaping survey study (IRB001196). Upon completion of the vaping survey study, participants are given the opportunity to share their contact information if they are interested in this study.

Community providers of care and services in Baltimore, Washington DC and the surrounding areas may be contacted for recruitment and IRB approved materials will be offered to these facilities. Additionally, some healthcare providers provide medical record recruitment services. These services include sending IRB approved notices to their potentially qualified patients, who have opted in for such messages, via their secure electronic patient portals (i.e., medical record) to let them know there is a research study for which they may qualify. If they are interested, patients will indicate that their information can be sent to the study team. Potential participants may also be recruited from the NIDA IRP approved screening protocol.

NIDA IRP personnel may hand out IRB approved materials, meet potential candidates interested in studies and answer any questions they may have. As done for previous outreach events, we may take NIH issued, password-protected devices so that interested people can leave their information with us. We will work with IT staff to ensure this system is compliant with NIDA-IRPs ISSO and will comply with Privacy Act requirements. Typically, IT staff will create a database for outreach personnel to record candidate information directly so that they cannot see other people's information. As a back-up, (e.g., battery failure) we may take index cards so that people can write down their information for us. Again, this method would eliminate the possibility that they would see anyone else's information as we would give each person their own card.

